I will conduct the trial in accordance with the clinical investigation plan, Good Clinical Practice guidelines, ISO 14155:2011 (Clinical Investigation of Medical Devices for Human Subjects - Good Clinical Practice), as well as local regulations. I also accept respective revisions to the clinical investigation plan approved by authorized personnel of the Sponsor and by regulatory authorities.

Institution:

[name] [name]

Principal Investigator (Printed name)

Principal Investigator (Signature)

22/2/18

Date

PROTOCOL SUMMARY

TITLE	Clinical Evaluation of the Safety and Performance of Fractional RF for the Treatment of Surgical Scars Following Breast Augmentation, Abdominoplasty or Face Lift
SUMMARY	Split-body/face evaluator-blind study of the safety and performance of fractional RF for the treatment of surgical scars following breast augmentation, abdominoplasty or face lift. The study will enroll up to 50 female subjects requesting treatment of surgical scars following breast augmentation or abdominoplasty and up to 25 male and female subjects requesting treatment of surgical scars following face lift surgery. Subjects will receive a total of three treatments of their surgical scars at one-month intervals on one side of the body or facial incision only. Subjects will be followed up at one, two, three and ten months after their last treatment. Analysis will be performed on all subjects who receive at least one treatment. Outcomes will be compared to the non-treated side.
OBJECTIVES	The objective of this clinical study is to evaluate the safety and performance of fractional RF for the treatment of surgical scars following breast augmentation, abdominoplasty or face lift.
ENDPOINT	
Primary performance endpoints
 
• Improvement of surgical scars at 3 months post-treatment as evaluated by independent blinded reviewer using the General Aesthetic Improvement Scale (GAIS) and Manchester Scar Scale (MSS).• Improvement of surgical scars at 10 months post-treatment as evaluated by independent blinded reviewer using the General Aesthetic Improvement Scale (GAIS) and Manchester Scar Scale (MSS). 
Secondary performance endpoints
 
• Improvement of surgical scars at 1 and 2 months post-treatment as evaluated by independent blinded reviewer using the General Aesthetic Improvement Scale (GAIS) and Manchester Scar Scale (MSS).• Assessment of surgical scars at 3 and 10 months post-treatment as evaluated by independent blinded reviewer using the Patient and Observer Scar Assessment Scale.• Assessment of surgical scars at 3 and 10 months post-treatment as evaluated by the subject using the Patient and Observer Scar Assessment Scale.• Subjects' assessment of satisfaction with the treatment at 3 and 10 months post-treatment. 
Safety endpoints
 
• Subject's assessment of discomfort and pain after treatment as measured by a 10 cm visual analog scale (VAS).• Subjects experiencing a treatment-related adverse event (AE) by 10 months post-treatment.
POPULATION	The study will enroll up to 50 female subjects requesting treatment of surgical scars following breast augmentation or abdominoplasty and up to 25 male and female subjects requesting treatment of surgical scars following face lift surgery.

PHASE	Post-marketing
NUMBER OF SITES	One site
DESCRIPTION OF DEVICE	The Venus Viva™ fractional RF device has been shown in clinical studies to improve various skin conditions related to aging and alter collagen structures such as wrinkles, rhytids and scars. The device utilizes a 160 pin tip to deliver fractional RF energy to the skin.
STUDY DURATION	Approximately fifteen months
PARTICIPANT DURATION	Twelve months

SCHEMATIC OF STUDY DESIGN

1 KEY ROLES

2 INTRODUCTION: BACKGROUND INFORMATION AND SCIENTIFIC RATIONALE

2.1 BACKGROUND INFORMATION

Skin laxity, facial texture irregularities such as post acne scars, and facial wrinkles, clinically referred to as rhytides, are common skin conditions in both men and women. The appearance of these types of facial irregularities can result in distress for people of all ages, causing them to turn to cosmetic treatments such as surgical procedures (e.g., face lifts) as well as non-surgical procedures including chemical or laser peels, non-ablative laser resurfacing, or dermabrasion.¹ These procedures are usually associated with prolonged recovery times as well as arduous side effects. To circumvent these issues, the use of non-invasive, nonsurgical approaches that do not require downtime are becoming the preferred method of choice for patients seeking cosmetic improvements. An innovative technique that was introduced to reduce facial wrinkles and rhytides is known as radiofrequency (RF).

One of the earliest procedures entailed using mono-polar RF², although bipolar and multi-polar RF devices have also been developed. The premise behind RF technology is dermal heating, which initiates the denaturation of collagen and the stimulation of neocollagenesis through the induction of inflammation that leads to the production of fibroblasts at the heated area and the subsequent development of new collagen.^{3,4} RF energy produces an oscillating electrical current that can penetrate the dermis and hypodermal tissues without disturbing the epidermal-dermal barrier. The generation of the heat energy is the result of the natural resistance that dermal tissue has to the movement of ions with an electromagnetic field. Accordingly, the oscillating electrical current causes collisions between charged ions that are transformed into heat energy.^{3,5} The production of heat energy through RF typically results in ablation, coagulation, and skin resurfacing.

Mono-polar RF devices were used initially for facial treatments, and although the results appeared to be promising, this approach was associated with serious pain as well as the high incidence of adverse events including second-degree burns that are caused by the deeply penetrating heat production of the single electrode.⁶ Bipolar and multi-polar RF devices allow the heat energy to be distributed more evenly with less depth-penetration, thereby resulting in less pain and improved safety profiles^{7,8} but concerns remained regarding the ability to precisely control the degree of ablation and coagulation that is required depending on a patient's skin type. Moreover, a randomized, blinded, split-face study comparing the use of mono-polar and bipolar RF devices for the treatment of skin laxity and wrinkles indicated that there was no difference in pain, side effects, or efficacy between mono-polar and bipolar devices.⁹ Therefore, RF techniques that improve the ability to control the ablation and coagulation of

the skin can result in treatment consistency that will provide more flexibility to treat a wider variety of skin conditions.

2.2 RATIONALE

Fractional RF technology has been shown in clinical studies to improve skin laxity, and to treat various skin conditions related to aging and alternate collagen structures such as wrinkles, rhytids and scars.

The objective of this clinical study is to evaluate the safety and performance of fractional RF for the treatment of surgical scars following breast augmentation, abdominoplasty or face lift.

The use of the Venus Viva™ has been determined to present non-significant risk in accordance with 21 CFR 812.3 for the intended use in this study, because the device is not:

- Intended as an implant;
- Purported or represented to be for use supporting or sustaining human life;
- Substantial importance in diagnosing, curing, mitigating, or treating disease, or otherwise preventing impairment of human health
- Otherwise presenting a potential for serious risk to the health, safety, or welfare of a subject.

This study will be conducted in compliance with the protocol and according to Good Clinical Practice (GCP) standards.

2.3 POTENTIAL RISKS AND BENEFITS

2.3.1 KNOWN POTENTIAL RISKS

The potential risks for adverse events of the treatment procedure include but are not limited to discomfort or significant pain post-treatment, excessive skin redness (erythema) and/or swelling (edema), in-grown hairs, damage to natural skin texture (crust, blister, burn), change of pigmentation (hyper- and hypo-pigmentation) and scarring. Treatment of hair-bearing areas in male patients may result in some damage to the follicles and subsequent loss of hair. Avoid the beard area and other hair-growing zones if the patient does not wish to experience hair growth reduction.

Further information about residual risks associated with the device and with participation in the clinical investigation are reported in the device User Manual.

Residual risks will be mitigated as follows:

- Selection of Investigator with experience in the therapeutic area of the clinical investigation
- Investigator will undergo training prior to patients' enrollment
- For the first procedure of each site, an experienced person with the use of the device, representing the sponsor, will attend.
- Patients will be rigorously screened prior to their enrollment
- Patients will be rigorously followed over the course of the study

2.3.2 KNOWN POTENTIAL BENEFITS

If the subject agrees to participate in this study, he/she will be contributing to the understanding of the device's impact and the biological processes that are occurring regarding surgical scar tissue. This

understanding may lead to optimization of the treatment with this device for these indications. In addition, the subject may benefit from improvement in surgical scar tissue in the treated areas.

3 OBJECTIVES AND PURPOSE

The study is being conducted to evaluate the safety and performance of fractional RF for the treatment of surgical scars following breast augmentation, abdominoplasty or face lift. Total expected duration of the clinical investigation is fifteen months (enrolment period of 3 months, follow-up period of 12 months), while individual subject participation will take 12 months.

4 STUDY DESIGN AND ENDPOINTS

4.1 DESCRIPTION OF THE STUDY DESIGN

This is a split-body/face evaluator-blind study of the safety and performance of fractional RF for the treatment of surgical scars following breast augmentation, abdominoplasty or face lift.

4.2.1 PRIMARY ENDPOINT

- The primary endpoints were chosen since it clearly links to the overall objectives of the study, that is, treating surgical scar tissue to improve appearance as evaluated by an independent blinded reviewer using the General Aesthetic Improvement Scale (GAIS) and Manchester Scar Scale (MSS) at 3 and 10 months post-treatment.

4.2.2 SECONDARY PERFORMANCE ENDPOINTS

- Improvement in appearance of surgical scars at 1 and 2 months post-treatment as evaluated by independent blinded reviewer using the General Aesthetic Improvement Scale (GAIS) and Manchester Scar Scale (MSS).
- Assessment of surgical scars at 3 and 10 months post-treatment as evaluated by independent blinded reviewer using the Patient and Observer Scar Assessment Scale (POSAS).
- Assessment of surgical scars at 3 and 10 months post-treatment as evaluated by the subject using the Patient and Observer Scar Assessment Scale (POSAS).
- Subjects' assessment of satisfaction (5-point Likert Scale) with the treatment at 3 and 10 months post-treatment.

Safety endpoints:

- Subject's assessment of discomfort and pain after treatment as measured by a 10 cm visual analog scale (VAS).
- Subjects experiencing a treatment-related adverse event (AE) by 10 months post-treatment.

4.2.3 EXPLORATORY ENDPOINTS

None

5 STUDY ENROLLMENT AND WITHDRAWAL

5.1 STUDY POPULATION

The study will enroll up to 50 female subjects requesting treatment of surgical scars following breast augmentation or abdominoplasty and up to 25 male and female subjects requesting treatment of surgical scars following face lift surgery.

5.2 PARTICIPANT INCLUSION CRITERIA

1. Healthy, female, subjects 20-60 years of age who are seeking treatment for their breast augmentation or abdominoplasty surgical scars or male and female patients 40-75 years of age who are seeking treatment for their face lift surgical scars.
2. A minimum of four weeks since surgery.
3. Able to read, understand and voluntarily provide written Informed Consent.
4. Able and willing to comply with the treatment/follow-up schedule and requirements.
5. Willing to avoid direct sunlight for the duration of the study.
6. Women of child-bearing age are required to be using a reliable method of birth control at least 3 months prior to study enrollment and for the duration of the study, and have a negative Urine Pregnancy test at baseline.

5.3 PARTICIPANT EXCLUSION CRITERIA

1. Fitzpatrick skin types 5-6.
2. Implantable defibrillators, cardiac pacemakers, and other metal implants
3. Subjects with any implantable metal device in the treatment area
4. Pacemaker or internal defibrillator, or any other active electrical implant anywhere in the body (e.g. cochlear implant).
5. Permanent implant in the treated area, such as metal plates and screws, or an injected chemical substance.
6. Current or history of any kind of cancer, or pre-malignant moles.
7. Severe concurrent conditions, such as cardiac disorders.
8. Pregnancy or intending to become pregnant during the study and nursing.
9. Impaired immune system due to immunosuppressive diseases, such as AIDS and HIV, or use of immunosuppressive medications.
10. History of diseases stimulated by heat, such as recurrent herpes simplex in the treatment area; may be enrolled only following a prophylactic regime.
11. Poorly controlled endocrine disorders, such as diabetes.
12. Any active condition in the treatment area, such as sores, psoriasis, eczema, and rash.
13. History of skin disorders, such as keloids, abnormal wound healing, as well as very dry and fragile skin.
14. History of bleeding coagulopathies, or use of anticoagulants.
15. Use of isotretinoin (Accutane®) within six months prior to treatment.
16. Treating over tattoo or permanent makeup.
17. Excessively tanned skin from sun, tanning beds or tanning creams within the last two weeks.
18. As per the practitioner's discretion, refrain from treating any condition which might make it unsafe for the patient.

5.4 STRATEGIES FOR RECRUITMENT AND RETENTION

Up to 50 female subjects with surgical scars due to breast augmentation or abdominoplasty and 25 male and female subjects with surgical scars due to face lift surgery will be enrolled at the single investigative site. It is anticipated that it will take up to fifteen months to complete the study. A qualified dermatologist or plastic surgeon will be the recruited to participate as an investigator. Subjects will be primarily be recruited primarily from the investigator's practice. Any advertising campaigns and materials will be reviewed and approved by an Ethics Committee or Institutional Review Board (EC or IRB) before implementation. Due to the long duration of the study, subjects will be contacted by the investigative site on a regular basis in order to enhance retention.

5.5 PARTICIPANT WITHDRAWAL OR TERMINATION

5.5.1 REASONS FOR WITHDRAWAL OR TERMINATION

Subjects are free to withdraw from participation in the study without prejudice at any time upon request. In the event that a subject drops out of the study or is withdrawn from the study, the End of Study/Early Discontinuation CRF form should be completed. On the discontinuation page, the Investigator should record the date of the withdrawal and the reason for withdrawal.

Reasonable effort should be made to contact any subject lost to follow up during the course of the study in order to complete assessments and retrieve any outstanding data. The records of subjects who terminate prior to completing the study will be retained and the reason for termination will be documented.

The investigator may terminate participation in the study if:

- Any clinical adverse event (AE), laboratory abnormality, or other medical condition or situation occurs such that continued participation in the study would not be in the best interest of the subject.
- The subject meets an exclusion criterion (either newly developed or not previously recognized) that precludes further study participation.

5.5.2 HANDLING OF PARTICIPANT WITHDRAWALS OR TERMINATION

Every effort will be made to continue follow-up of withdrawn or terminated subjects or subjects who discontinue the intervention but remain in the study for follow-up, especially for safety and performance study endpoints. Every effort will be made to conduct an exit visit (final study visit, see section 7.3.5) to withdrawn patients, and to undertake protocol-specified safety follow-up procedures to capture AEs, serious adverse events (SAEs) and device deficiencies.

5.6 PREMATURE TERMINATION OR SUSPENSION OF STUDY

The sponsor may suspend or prematurely terminate this study at the investigation site for significant and documented reasons.

The principal investigator, EC/IRB, or regulatory authority may suspend or prematurely terminate participation in the study at the investigation site for which they are responsible.

If suspicion of an unacceptable risk to subjects arises during the study, or when so instructed by the EC/IRB or regulatory authorities, the sponsor shall suspend the clinical investigation while the risk is assessed. The sponsor shall terminate the study if an unacceptable risk is confirmed.

The sponsor shall consider terminating or suspending the participation of the investigation site or investigator in the study if monitoring or auditing identifies serious or repeated deviations on the part of an investigator.

If suspension or premature termination occurs, the terminating party shall justify its decision in writing and promptly inform the other parties with whom they are in direct communication. The principal investigator and sponsor shall keep each other informed of any communication received from either the EC/IRB or the regulatory authority.

If, for any reason, the sponsor suspends or prematurely terminates the study at the investigation site, the sponsor shall inform the responsible regulatory authority as appropriate and ensure that the EC/IRB is notified, either by the principal investigator or by the sponsor. If the suspension or premature termination was in the interest of safety, the sponsor shall inform all other principal investigators.

If suspension or premature termination occurs,

- a) the sponsor shall remain responsible for providing resources to fulfil the obligations from the clinical investigative plan and existing agreements for following up the subjects enrolled in the study, and
- b) the principal investigator or authorized designee shall promptly inform the enrolled subjects at the investigation site, if appropriate

In case of early termination, final study activities according to the protocol, including the follow up visits and procedures to assess the safety and efficacy of the device will be conducted, regardless of the sponsor's interest in the study. Follow-up activities will be conducted so that device deficiencies can be identified and appropriate safety measures can be implemented.

At the completion or termination of the study, the Investigator will return all remaining clinical supplies to Sponsor along with a copy of the device supply and inventory records.

Circumstances that may warrant termination or suspension include, but are not limited to:

- Determination of unexpected, significant, or unacceptable risk to participants (examples of findings that might trigger a safety review are the number of SAEs overall, the number of occurrences of a particular type of SAE, severe AEs/reactions, or increased frequency of events – refer to section 8.5 STUDY HALTING RULES).
- Demonstration of performance that would warrant stopping
- Insufficient compliance to protocol requirements
- Data that are not sufficiently complete and/or evaluable
- Determination of futility

Study may resume once concerns about safety, protocol compliance, data quality are addressed and satisfy the sponsor, EC / IRB and/or regulatory authorities.

6 INVESTIGATIONAL DEVICE

6.1 INVESTIGATIONAL DEVICE AND CONTROL DESCRIPTION

6.1.1 ACQUISITION

If the investigative site does not own a Venus Viva™, a device will be provided by the sponsor. An activation code will be required to activate the device (not applicable if the site owns the device). This code will not be provided to the investigative site until all regulatory and EC or IRB approvals are in place and the site has received training for both the device and the study (if applicable).

6.1.2 DEVICE SPECIFIC CONSIDERATIONS

- Device model(s) - Venus Viva™
- Device settings and programming – 240-280 volts, 15-20 ms pulse duration
- Duration of exposure and frequency – single pass, monthly for 3 months

The Venus Viva™ is a non-invasive medical aesthetic device, intended for use in dermatologic and general surgical procedures, requiring ablation and resurfacing of the skin, using the Viva applicator.

The system consists of a handheld applicator with disposable tips. The tip consists of 160 pins, 8x20 mm in size, that delivers the Multi Polar Radiofrequency (RF) to the skin. Further details about the Venus Viva™ can be found in the device User Manual.

6.2 INVESTIGATIONAL DEVICE ACCOUNTABILITY PROCEDURES

If the device is supplied by the sponsor, traceability shall be achieved during and after the clinical investigation by assignment of serial numbers to device and applicators. Disposal tips will be provided by the sponsor.

7 STUDY PROCEDURES AND SCHEDULE

7.1 STUDY PROCEDURES/EVALUATIONS

7.1.1 STUDY SPECIFIC PROCEDURES

The following procedures and evaluations will be done as part of the study:

Demographics

Medical /surgical history (obtained by interview and/or medical records)

Physical examination

Assessment of eligibility

Vital signs [weight, temperature, respiratory rate, heart rate and blood pressure]

Photographs

Blinded assessment

Administration of questionnaires and scales for blinded reviewer and patient-reported outcomes

Adverse event recording

Concomitant medications

7.2 LABORATORY PROCEDURES/EVALUATIONS

7.2.1 CLINICAL LABORATORY EVALUATIONS

Urine pregnancy test to be performed within 24 hours of study intervention with results available prior to administration of treatment.

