7.3 STUDY SCHEDULE

7.3.1 SCREENING

Visit 1, Day -1 (Skin Types I-III) or Day -5 (Skin Type IV)

Point of enrollment

Point of enrollment is defined as the point where the patient, after having signed the informed consent form, is confirmed to fulfill all criteria for eligibility.

Following the point of enrollment, each subject will receive study treatment and study questionnaires.

Screening Visit

If the subject meets the preliminary study criteria, the study doctor, and/or his/her designee, will obtain an informed consent from the subject prior to any study procedure, clearly indicating his/her understanding of the requirements and possible risks associated with study participation and other applicable treatment options.

During the first visit, the study investigator, and/or his/her designee, will screen the subject for eligibility to participate in the clinical study using the inclusion/exclusion criteria. A urine sample for the pregnancy test will be obtained (in patients of child-bearing potential). During screening, the study doctor will review the subject's medical/surgical history and examine the subject's targeted area to ensure that it meets the study criteria. The subject will complete screening and the treatment will be scheduled.

During the first visit, the investigator will ask women of child-bearing potential for the date of their last period, if not applicable the investigator shall inquire about the form of contraceptive they use to confirm they meet the inclusion criteria.

Test Spots

A small test spot will be performed in a non-conspicuous area of the treatment site, prior to the first complete session. Test spots are performed to establish the following requirements:

- Confirm the patient's suitability for treatment: For skin types I-III wait 24-48 hours before assessing the skin response and 5-7 days for skin type IV.

- Establish and confirm treatment parameters: If the desired endpoint of erythema and edema – in a tip-shaped pattern – has not been achieved within 10-15 minutes, increase the RF indicator level and perform another test spot. If the response is excessive, decrease the parameters and perform another test spot.

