Test spot results will indicate if the patient can tolerate the treatment without developing adverse effects. According to patient tolerance to the test spot, you may determine treatment parameters and whether anesthesia is needed. In addition, it is advisable to perform a test spot whenever changing parameters.

Treatment

Shave any hair in the treatment area. Ensure that the skin is completely dry during the entire treatment. If the skin moistens during treatment (i.e. perspiration, etc.) re-wipe the skin with an alcohol pad and ensure that the skin is completely dry before continuing the treatment.

Set the treatment parameters (Voltage 240-280, 15-20 ms pulse duration). Set the desired energy level according to the skin type, severity of the treated condition, treatment area, bone proximity, etc. Set conservative parameters from a test spot for the first treatment, and then gradually increase during treatment or in subsequent treatments according to the desired impact and test spot results.

Select the desired tip pattern to Full or Half if the tip extends beyond the boundary of the scar tissue in order to restrict treatment to the scar tissue. Treatment consists of a single pass over the treatment area, however, the test spot will consist of a single pulse. Adjust the treatment parameters according to the test spot response. To perform the treatment, place the tip on the target zone, perpendicular to the skin surface and with full contact with the skin. Emit a pulse by pressing the applicator's trigger; this will create a tip-shaped pattern on the patient's skin that will appear 1-2 minutes later. Move the applicator to an adjacent spot on the skin overlapping by 10% and emit another pulse (not applicable to the test spot). There should be no untreated gaps between the pulses.

Examine the treated area. The immediate responses, indicative of the desired effect, are erythema and edema in the immediate area of the tip-shaped pattern and possibly also around it. The edema usually appears 1-2 minutes after pulsing and reaches its peak (of up to moderate edema) within 30 minutes. It should be noted that erythema is not easily noticeable – if at all – in darker skin types. Therefore, the edema will be more prominent in these patients. After completing a full pass on the entire treatment area, if untreated patches of skin are apparent, re-treat these patches as per the following procedure:

- Wipe the untreated patch of skin with a dry gauze pad.

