- Treat the untreated patches of skin as normally.

Fine-tuning of the parameters should be done before proceeding to treatment of the entire sub-area with the selected parameters. Treatment consists of a single pass over the designated area. The applicator tip should be placed on the skin, a pulse emitted, then lifted and moved to an adjacent spot of the skin. The emitted pulses should create tip-shaped patterns. Leave, no untreated gaps between the pattern marks, while also being careful not to overlap the treated zones. The parameters can be modified during subsequent visits, as per the practitioner's discretion.

Post-Treatment Care

Post-treatment cooling is not necessary. In the event of post-treatment discomfort, it is recommended to cool the treated area immediately with air cooling. Cold (not frozen) packs may also be used.

Blistered or ulcerated skin can be treated with a prescribed cream. Tiny scabs of less than 1 mm diameter will usually form 24-72 hours post-treatment and may remain for several days. The scabs should not be touched or scratched even if they itch, and should be allowed to shed off naturally. Blistered or ulcerated skin can be treated with a prescribed antibiotic ointment or burn treatment cream as per physician's discretion. During the first two days following treatment, care should be taken to prevent trauma to the treated site. Hot baths, massage, etc. should be avoided. The skin should be kept clean to avoid contamination or infection. Any mechanical or thermal damage to the area must be avoided. Moisturizer may be applied only 24 hours after each treatment, and then should be applied regularly throughout the course of the treatment. Make-up may be applied only 24 hours after each treatment if desired, unless an unwanted reaction occurs in the area. Generally, 24 hours after treatment, patients may use regular soaps, but not scrub soaps or exfoliants. The patient should use a high-factor sunscreen (at least 30 SPF) and protect the treated area from sunlight for at least one month after the treatment. Tanning of any sort (sun exposure, tanning beds, and artificial sunless tanning lotions) is not allowed in the treated areas during the entire course of the treatment. Tanning after treatment may cause hyperpigmentation.

The patient should return 1-2 days for skin types I-III or 5-7 days for skin type IV after the test spot treatment to ensure that no adverse events have occurred.

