7.3.2 ENROLLMENT/BASELINE

Enrollment/Baseline Visit (Visit 2, Day 0)

Once a subject has been confirmed that they continue to meet inclusion/exclusion criteria, they will receive a unique identifying number that will be composed of a two-digit site number and a two-digit subject number in sequence. This unique identifier will be used throughout the entire study and will be entered in the subject's case report form (CRF). The investigator will confirm that the subject still meets the inclusion/exclusion criteria. Vital signs and demographics will be collected and a physical exam will be performed. The subject will complete the POSAS.

Photography

Photographs will be taken prior to first treatment and throughout the study according to specified time points detailed in the Schedule of Events Table (section 7.3.7), utilizing standard scientific equipment. Two sets of photographs will be required, one set for the treated side of the body/face and a second set for the untreated side of the body/face.

The photos should be taken in a private room or area of the clinic under controlled conditions, including the distance, angle, background and lighting in order to achieve high-quality sets of photographs. Direct illumination will not be used. The subject should be placed in the same position each time. As each photograph is taken, it should be viewed to ensure that it is in focus and is similar to its baseline counterpart in all technical aspects, including lighting, distance and angle.

For consistency purposes, the same person should ideally take all study photographs, especially per subject. The digital files should follow a consistent standard naming scheme.

Treatment

Subjects will receive treatment as described in section 7.3.1. Only one side of the body/face will be treated. The same side will be treated for the duration of the study. Only half of a scar will be treated

and remaining half will serve as the control. Following treatment, the investigator will examine the treated area and report immediate and short term response. Subjects will complete the 10 cm discomfort/pain VAS immediately after treatment. A new disposal tip will be used for each patient treatment.

Treatment procedure should include positioning of the patient in a manner that enables comfortable access to the treated anatomical site.

Assessment

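### The 24-hour pregnancy-test rule in section 7.2.1 is not carried into the visit text: the only test named is at Visit 1, which for skin type IV is 5-7 days before the first full treatment

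*Combined protocol and SAP*

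**What the plan says.** Section 7.2.1 states the timing rule: "Urine pregnancy test to be performed within 24 hours of study intervention with results available prior to administration of treatment". It does not define *study intervention*.

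Section 7.3.1 times screening as "Visit 1, Day -1 (Skin Types I-III) or Day -5 (Skin Type IV"), and among the procedures of that first visit it says: "A urine sample for the pregnancy test will be obtained (in patients of child-bearing potential"). A test spot is also made before the first full session, and its result has to be awaited: "For skin types I-III wait 24-48 hours before assessing the skin response and 5-7 days for skin type IV". The post-treatment care text in the same section gives the matching return interval: "The patient should return 1-2 days for skin types I-III or 5-7 days for skin type IV after the test spot treatment".

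Section 7.3.2, headed "Enrollment/Baseline Visit (Visit 2, Day 0"), describes the visit of the first full treatment. It lists vital signs, demographics, physical examination, the subject's POSAS, photographs and treatment. It names no pregnancy test, but does say: "The investigator will confirm that the subject still meets the inclusion/exclusion criteria".

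Three related provisions matter. Inclusion criterion 6 (section 5.2) asks for a negative urine test at baseline. Section 5.3 makes pregnancy an exclusion and rules out only Fitzpatrick types 5-6, so type IV women are eligible. Section 8.4.4 ends participation for a subject who becomes pregnant.

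**The concern.** A site schedules its work from the visit text. If the visit text asks for one test, at screening, and screening is several days before treatment, the site will treat on a result older than section 7.2.1 allows, and nothing at Visit 2 explicitly tells it to retest.

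What is at stake is compliance with a safety limit that the protocol sets for itself, on a condition that it treats as both an exclusion and a reason for termination. An early pregnancy missed at screening, or one that begins between the visits, would not be picked up by a scheduled test before the first full treatment. No statistical property of the trial is involved.

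**Working it through.** The plan gives no figure to reproduce. The check compares the limit with the interval between the scheduled test and the first full treatment.

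**Inputs**

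- Limit: 24 h (section 7.2.1).
- Scheduled test: Visit 1 (section 7.3.1).
- First full treatment: Visit 2, Day 0 (section 7.3.2).
- Interval from Visit 1 to Visit 2: 5-7 days for type IV and 24-48 h for types I-III (section 7.3.1, test-spot wait and return interval).

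**Formulas**

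- Age of test at treatment = interval in days × 24 h.
- Excess = age − 24 h.
- Ratio = age ÷ 24 h.

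| Skin type | Age of test | Excess over limit | Ratio to limit |
|---|---|---|---|
| IV | 5 × 24 = 120 h to 7 × 24 = 168 h | 120 − 24 = 96 h to 168 − 24 = 144 h | 120/24 = 5 to 168/24 = 7 |
| I-III | 24 h to 48 h | 24 − 24 = 0 h to 48 − 24 = 24 h | 24/24 = 1 to 48/24 = 2 |

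For type IV, no interval that the visit text allows brings the Visit 1 test inside 24 hours of the Visit 2 treatment. For types I-III the nominal Day -1 timing is at the limit, and only the upper part of the wait goes past it.

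**Which event starts the clock?** If *study intervention* is the Visit 1 test spot, test and intervention fall at the same visit and the excess is 0 h for every skin type. The wording favours the Visit 2 treatment:

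- Section 7.2.1 itself ties the result to the giving of treatment.
- Section 7.3.1 separates the two acts: "Treatment consists of a single pass over the treatment area, however, the test spot will consist of a single pulse".
- Section 10.4.1 defines baseline by reference to a first treatment at Visit 2.

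Against this, section 7.3.1 once calls the test spot a treatment (in the return-interval sentence quoted above), and section 13.3.1 speaks of starting intervention with the device, which could include the test spot.

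**Does *baseline* in criterion 6 settle the day?** It does not. Section 7.3.2 uses the label for Visit 2, while the column heading in the section 7.3.7 table uses it for Visit 1.

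**The case against.** The strongest reply is that the sections do not conflict. Section 7.2.1 is an instruction in its own right and binds the site together with section 7.3. Nothing forbids a second test, so a site that reads both can comply by adding one at Visit 2. The eligibility re-check at Visit 2, read with criterion 6 and section 7.2.1, also points to a retest. This stands in part. A reader might infer that the two texts cannot both be obeyed, and the documents do not support that. What remains is that the re-check names no test, and that a site holding a negative Visit 1 result could reasonably regard criterion 6 as met.

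The second reply is the test-spot reading, which removes the excess altogether. It cannot be excluded, because the term is undefined, but it fits poorly with the rest of the sentence in section 7.2.1.

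The third concerns the schedule table. A reader might infer from it that no test is planned at Visit 2. That inference is not safe. In the text available, the pain VAS and investigator-response rows show marks at Visits 1, 3 and 5, although the visit text places these assessments at Visits 2, 4 and 6. The position of the pregnancy-test mark is therefore not used here.

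Finally, the practical risk is limited. Reliable contraception is required from at least three months before enrollment, the date of the last period is asked for at the first visit, and the risk lists in sections 2.3.1 and 8.2.3 name no harm specific to pregnancy. All of this stands, and it keeps the point minor.

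**Conclusion.** The point holds as a minor inconsistency between a stated safety limit and the visit schedule. On the natural reading, in which *study intervention* means the Visit 2 treatment, the only test named in the visit text is 96-144 hours too old for skin type IV. If the term means the test spot, there is no excess.

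A reader might extend the breach to all skin types. The documents support it firmly only for type IV; for types I-III it arises only when the wait runs beyond 24 hours. A reader might also conclude that pregnant women would be treated or harmed, but nothing in the documents quantifies either, and the number of type IV women of child-bearing potential is not given.

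The visit text names no test before the Month 1 and Month 2 treatments either. Whether section 7.2.1 reaches them is open, so no breach is claimed there.

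**What to change.** 1. Keep the Visit 1 test, which also covers the test spot.
2. In section 7.3.2, add a urine pregnancy test on Day 0 for women of child-bearing potential, with a negative result required before treatment. Mark it in the schedule table at Visit 2 if it is not already shown there.
3. In section 7.2.1, keep the 24-hour rule and add that it applies to the Visit 2 treatment. Do not reword it to cover the first treatment only: that could remove protection that the present wording may give to the test spot and to the Month 1 and Month 2 treatments.

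The cost is one extra urine test per woman of child-bearing potential, at a visit that already takes place. The upper bound is 50 + 25 = 75 tests. The true number will be lower, because the face-lift group includes men and is aged 40-75. The text changes are one line in section 7.3.2, one clarifying phrase in section 7.2.1 and at most one table mark.
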